#### **4.8.2 Secondary Endpoints: Virologic Endpoints [IRCRSLTS] (PEP and ITT)**

Viral shedding will be assessed by quantitative RT-PCR (reported as  $\log_{10}$  RNA copies/mL) with measurements obtained on Days 0, 3, and 7. These measurements will be used to define the following variables:

- a. Figure and associated table showing number (%) of subjects who had values  $<LOD$ ,  $LOD-<LLOQ$ ,  $\geq LLOQ$  at each visit.
- b. Figure and associated table showing number of subjects and minimum, maximum, median, 25% and 75% percentile of the value of viral shedding at each visit (subjects with values  $<LOD$  will be ranked as lower than detectable values in this analysis; minimum and maximum in table only). Comparison of randomized arms at each of Day 3 and Day 7 will be based on the extension of Wilcoxon's test to handle censoring of measurements which are  $<LLOQ$ .
- c. Number (%) of subjects with undetectable viral load at both Day 3 and Day 7; detectable at Day 3 and undetectable at Day 7; detectable at Day 7 (irrespective of whether or not detectable at Day 3). Analysis will be restricted to subjects with measurements at both Day 3 and Day 7. Comparison of percentages of subjects in this table using the Wilcoxon Test.
- d. Above tables/figures/analyses will be repeated for the subset of subjects who had detectable viral load at Day 0.

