##### 4.8.1 Primary Endpoint [IRCRSLT] (population for the primary analysis and PEP)

The primary endpoint is defined as the percentage of subjects shedding virus by PCR in nasopharyngeal swabs obtained at Day 3.

- a. Completeness of viral shedding results showing number (%) at Day 0, 3 and 7 who:
  - had qPCR result
  - were lost to follow-up prior to the visit
  - were in follow-up but had missing value
- b. Primary Analysis: Among subjects with Day 3 qPCR results, number (%) with detectable viral shedding at Day 3. Comparison of randomized arms with associated 95% confidence interval and p-value based on the normal approximation to the binomial distribution.

- c. Sensitivity Analyses (PEP only): to assess potential impact of missing measurements. Repeat the primary analysis (above) considering missing measurements in turn as (a) above the limit of detection, or (b) below the limit of detection, or (c) above the limit of detection in one randomized arm and below in the other arm (so as to maximize the difference between arms), or (d) the opposite of (c) (so as to minimize the difference between arms).
- d. Sensitivity Analyses (PEP only): Repeat the primary analysis above but restricted (a) to samples in which one or more housekeeping genes had detectable levels (hence indicating adequate sample); and (b) to samples in which all housekeeping genes had detectable levels.
- e. Subgroup Analyses (PEP only): Comparison of randomized treatments will be undertaken by sex (male vs female), influenza type (A vs B), and country/race (US/white vs US/non-white vs Thailand vs other countries). To assess whether the difference between randomized treatments varies by subgroup, a treatment by subgroup interaction test will be undertaken using logistic regression.

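### The Day 3 and Day 7 viral-load test in SAP 4.8.2b names only the LLOQ as its censoring threshold, so read plainly it ties undetectable with detectable-but-unquantifiable samples and gives up some power

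*SAP*

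**What the plan says.** SAP 4.8.2 handles the quantitative PCR results from team-collected nasopharyngeal swabs in four items.

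- **Item a** ("Figure and associated table showing number (%) of subjects who had values" in each class) tabulates three ordered classes at each visit: below LOD, LOD to below LLOQ, and at or above LLOQ.
- **Item b** gives percentiles at each visit and says that subjects below LOD "will be ranked as lower than detectable values in this analysis". Its next sentence sets the test: "Comparison of randomized arms at each of Day 3 and Day 7 will be based on the extension of Wilcoxon's test to handle censoring" of values below LLOQ. It names no specific test and does not say whether the two classes below LLOQ get separate bounds.
- **Item c** groups subjects by detectability pattern ("undetectable viral load at both Day 3 and Day 7; detectable at Day 3 and undetectable at Day 7", or detectable at Day 7) and compares arms with a Wilcoxon test.
- **Item d** repeats these for subjects with detectable virus at Day 0.

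The primary analysis in SAP 4.8.1 uses the LOD: "Among subjects with Day 3 qPCR results, number (%) with detectable viral shedding at Day 3". So do its missing-data sensitivity analyses, for example "above the limit of detection in one randomized arm and below in the other arm".

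**The concern.** Two adjacent sentences of item b use different cut-offs. The summary separates undetectable from detectable samples. The test that supplies the p-value is described only by the LLOQ. If every result below LLOQ is entered as one left-censored value, the test cannot order an undetected sample against a detected but unquantified one, although the laboratory has reported which is which.

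Item b is the only between-arm test of quantitative viral load listed in SAP 4.8.2. It is run at two visits and in two populations. A drug that moves samples from low positive to negative would earn no credit in it for that movement. The stake is sensitivity in this secondary comparison, and a p-value that may not match the figure beside it.

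**Working it through.** **1. The plan's own figure.** No power figure is stated for the item b test. The nearest is Protocol 9.2.1, Table 9: 42.5% v 57.5%, 90% power, two-sided 0.05, total 490, or 546 with 10% missing.

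- Per arm, n = [1.960 x sqrt(2 x 0.5 x 0.5) + 1.282 x sqrt(0.425 x 0.575 + 0.575 x 0.425)]^2 / 0.15^2 = 231.4, so 232 per arm and 464 in total.
- With continuity correction, (231.4 / 4) x [1 + sqrt(1 + 4 / (231.4 x 0.15))]^2 = 244.6, so 245 per arm and **490** in total.
- 490 / 0.9 = 544.4, so 545 against the stated 546 (546 is the next even number).
- Exact two-sided Fisher power at 490 is 90.3%.

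The design inputs therefore reproduce and can be carried over to item b.

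**2. How the test scores a pair.** A Gehan-type Wilcoxon extension compares each oseltamivir subject with each placebo subject. It scores +1 or -1 if the order is known and 0 if it is not.

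| Pair | One bound at LLOQ | Three ordered classes |
|---|---|---|
| below LOD v LOD to LLOQ | 0 | +1 or -1 |
| below LOD v quantified | +1 or -1 | +1 or -1 |
| LOD to LLOQ v quantified | +1 or -1 | +1 or -1 |
| same class below LLOQ | 0 | 0 |

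Only the first row differs. Let f be the share of detectable samples below LLOQ and, for this step only, take f as equal in both arms. The share of cross-arm pairs that loses its order is 0.425 x 0.425f + 0.575 x 0.575f = 0.511f. That is about 5%, 13%, 26% and 36% of pairs at f = 10%, 25%, 50% and 70%.

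**3. Sample size for item b.** SAP 4.8 includes the 50 pilot subjects in secondary efficacy analyses: 560 x 0.9 / 2 = 252 per arm, before exclusions for the Primary Efficacy Population. Protocol 9.5 excludes them: 510 x 0.9 / 2 = 229.5, about 230 per arm.

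**4. Power at Day 3.** I simulated normal latent log10 loads of equal variance. Arm means were set to give 57.5% and 42.5% above LOD, and LLOQ was set to give the stated pooled f. The test was a tie-corrected Mann-Whitney test, two-sided 0.05, with 8,000 replicates (simulation error about half a point). f is assumed, because the documents give neither LOD, LLOQ nor f.

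| f | Three classes, 252 per arm | Tied below LLOQ, 252 per arm | Loss (points) |
|---|---|---|---|
| 10% | 97% | 96% | 1 |
| 25% | 96% | 94% | 2 |
| 50% | 96% | 89% | 7 |
| 70% | 96% | 80% | 17 |

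At 230 per arm a separate run of 4,000 replicates gave 95% v 94% at f = 10%, 95% v 92% at 30%, 95% v 87% at 50% and 95% v 82% at 60%.

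**5. Limiting case.** Suppose treatment only moves samples between LOD-to-LLOQ and below LOD, so that the quantified share is equal in both arms. At 230 per arm and f = 20-60%, power is 44-66% with three classes and about 5% (the test's alpha) with ties.

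**6. Day 7.** The documents give no Day 7 detection rate. With 25% v 15% detectable assumed, 252 per arm and the same model, power is 82-83% with three classes. With ties it is 81%, 76%, 66% and 51% at f = 10%, 25%, 50% and 70%, a loss of about 2, 7, 17 and 31 points.

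**The case against.** **The tie is inferred.** Item b names no test and gives no bounds. A censored-data Wilcoxon could take samples below LOD as left-censored at LOD and those from LOD to LLOQ as interval-censored, which keeps the order. The ranking rule in the preceding sentence might also be meant to govern the test. This stands: one bound at LLOQ is the natural reading but not the only one. On either reading, the sentence needs to say how the two classes are scored.

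**A reader might infer that the plan discards the LOD distinction behind the primary endpoint.** The documents do not support that. The primary analysis tests "number (%) with detectable viral shedding at Day 3", its sensitivity analyses use the LOD, and item c carries detectability at both visits into a formal comparison. Only item b and its repeat in item d are affected.

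**A reader might infer that most late samples lie between LOD and LLOQ, so that the loss must be large.** The documents do not support that either. Protocol 9.2.1 puts about half of Day 3 samples below LOD and says nothing about how many of the rest are unquantifiable. The large losses need an assumed share of 50% or more, and the 31-point figure also needs an assumed Day 7 effect.

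**Censoring at the quantification limit is a recognised choice, and a display may use finer ranks than a test.** Both are true, so this is an inefficiency and not an error. It is most defensible when the laboratory reports only that a value is below LLOQ. Here the class below LOD is reported separately, so using the order needs no added assumption.

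**Conclusion.** The point holds as a minor one. The LLOQ is the only threshold that SAP 4.8.2b gives for its arm comparison. On the plain single-bound reading, the test drops an ordering that the assay supplies and that the summary in the same item uses. The cost is power in one secondary test and its repeat. The comparison stays valid: neither bias nor type I error inflation follows, and no stated sample size or primary result changes.

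At Day 3, with 252 per arm and 57.5% v 42.5% detectable, the loss is about 1 to 3 points if 10-25% of detectable samples are below LLOQ, and about 7 to 17 points if 50-70% are. This rests on the single-bound reading, a normal shift model, 10% missing results, no exclusions for the Primary Efficacy Population, and an LLOQ share that the documents do not give. Day 7 losses may be larger, but both the detection rates and the effect there are assumptions.

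**What to change.** In SAP 4.8.2b, state that the Day 3 and Day 7 arm comparison is a tie-corrected Wilcoxon rank-sum test on ordered values: all results below LOD tied lowest, all results from LOD to below LLOQ tied next, then quantified results ranked by log10 copies/mL. This is consistent with the ranking already stated for the summary. Apply the same scoring in the 4.8.2d repeat. The LLOQ-censored version may be kept as a sensitivity analysis, with its bounds stated.

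The cost is one sentence in the SAP, best settled before unblinding. It needs no new data or assay work and loses no subjects.

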### **Secondary Endpoints**

#### Clinical Endpoints:

- Time to alleviation of influenza clinical symptoms
- Time to absence of fever
- Time to resumption of normal activity
  - Note: in this analysis, the following endpoints will be used to represent “resumption of normal activity”:
    - Time to feeling as good as before the onset of the influenza illness (as measured by a global assessment question)
    - Time to return to pre-influenza illness level of function (as measured by a global assessment question)
    - Time to return to pre-influenza illness level of physical function (as measured by SF-36 physical score)
- Number of premature study treatment discontinuations
- Proportion of subjects who develop bronchitis, pneumonia, or other complications of influenza
- Proportion of subjects who require hospitalization
- 28-day mortality

Virologic Endpoints: (assessed by PCR in NP swab)

- Duration of viral shedding
- Change in viral shedding as a function of time
- AUC of viral shedding
- Frequency of emergence of antiviral resistance

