#### 4.3.4 Virology Measures (ITT and PEP) [team collected swabs]

- a. Viral shedding in nasopharyngeal (NP) swab by qPCR: number (%) <LOD, LOD-<LLOQ, ≥LLOQ, and summary of quantitative values on log10 scale [IRCRSLTS]
- b. Housekeeping (HK) gene levels by qPCR: number (%) <LOD, LOD-<LLOQ, ≥LLOQ-≤ULOQ, >ULOQ, and summary of quantitative values on log10 scale [IRCRSLTS]
- c. Viral shedding in nasopharyngeal (NP) swab by qPCR by housekeeping gene detection [IRCRSLTS]:

- NP virus <LOD: % HK <LOD, % HK LOD-<LLOQ, % HK  $\geq$ LLOQ- $\leq$ ULOQ, % HK >ULOQ
- NP virus LOD-<LLOQ: % HK <LOD, % HK LOD-<LLOQ, % HK  $\geq$ LLOQ- $\leq$ ULOQ, % HK >ULOQ
- NP virus  $\geq$ LLOQ: % HK <LOD, % HK LOD-<LLOQ, % HK  $\geq$ LLOQ- $\leq$ ULOQ, % HK >ULOQ

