- d. Global assessment: Times to “feeling as good as you did before you had the flu” and “functioning as well as you did before you had the flu” will be defined as the times of two successive measurements with “yes” responses to the respective global assessment questions.
- The details of the definition, handling of missing values and analysis will follow that for duration of clinical symptoms.
- e. Functional status: This is assessed using the 10-item domain of Physical Function from the SF-36, and calculated as the average of the scores of all 10 items. Functional status is evaluated daily through to Day 14 and then at Day 28.
- Scoring, including handling of missing values, will be undertaken per the standard instructions for the RAND 36-Item Health Survey 1.0 instrument (located at: [http://www.rand.org/health/surveys\\_tools/mos/mos\\_core\\_36item\\_scoring.htm](http://www.rand.org/health/surveys_tools/mos/mos_core_36item_scoring.htm) 1). If all 10 components are not scored, the pre-illness functional status will be scored as missing.
  - Figure and associated Table: Median, 25th and 75th percentiles, (and min and max value in table), with sample size, at each required measurement time.
  - Figure and associated Table: Median, 25th and 75th percentiles, (and min and max value in table), with sample size, change from Day 0 at each required measurement time.

- Statistical comparison between randomized arms of changes in score will be undertaken at Days 3, 7, 14 and 28 using Wilcoxon's test.
  - Time to return of physical function to pre-illness level is defined as the time from Day 0 to the first of two successive measurements at which the physical function score equals or is better than the pre-illness score (obtained by recall at enrollment). Time will be calculated in daily increments through to Day 14. For the purposes of defining the endpoint, if a subject's Day 0 and Day 1 assessments satisfy this criterion, then the duration will be set to zero. Missing values will be ignored. Times will be considered as discrete (i.e. based on the schedule of completion of diary cards) and subjects not having two successive assessments with scores equal to or better than the pre-illness score will be censored immediately after Day 14 (the last scheduled measurement time on which an endpoint can occur).

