- g. AUCs will be calculated for the self-collected swabs. This is defined as the area below the line formed by joining the measured values at each successive scheduled measurement time and above the limit of detection. This will be calculated using the trapezoidal rule. Missing values will be ignored (this is equivalent to imputing a missing value using linear interpolation between the previous and succeeding available values). If the Day 0 value is missing, then the subject will be excluded from the analysis.
  - Figure and associated table showing number of subjects and minimum, maximum, median, 25% and 75% percentile of the value of viral shedding at each scheduled measurement time. This will be presented (a) imputing values

as defined above for the calculation of AUC, and (b) using observed values only.

- Table showing number of subjects and minimum, maximum, median, 25% and 75% percentile of the AUC, both over all subjects and by strata defined by quartile of Day 0 measurement.
- P-value comparing randomized arms from Wilcoxon rank sum test stratified by quartile of Day 0 measurement.

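### The NP viral-load comparisons at Day 3 and Day 7 are not adjusted for Day 0 load, and no change-from-Day-0 or longitudinal comparison is named for the listed change-over-time endpoint

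*SAP*

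**What the plan says.** Protocol 3.3.2 and the SAP's summary of endpoints list "Change in viral shedding as a function of time" among the secondary virologic endpoints, assessed by PCR in NP swab. Protocol 3.3.3 defines several endpoints but not this one.

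SAP 4.8.2 builds its analyses on quantitative RT-PCR "with measurements obtained on Days 0, 3, and 7":

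- **Item b:** "Comparison of randomized arms at each of Day 3 and Day 7 will be based on the extension" of Wilcoxon's test for values below LLOQ. The two visits are tested separately.
- **Item c:** subjects are sorted into three ordered groups by detection at Days 3 and 7. "Comparison of percentages of subjects in this table using the Wilcoxon Test".
- **Item d:** "Above tables/figures/analyses will be repeated for the subset of subjects who had detectable viral load at Day 0".

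Day 0 load is available. SAP 4.3.4 tabulates "Viral shedding in nasopharyngeal (NP) swab by qPCR" at Day 0, including the log10 values.

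Two other SAP analyses do use baseline. For the self-swab AUC (4.10 item g): "P-value comparing randomized arms from Wilcoxon rank sum test stratified by quartile of Day 0 measurement". For functional status (4.9 item e): "Statistical comparison between randomized arms of changes in score will be undertaken at Days 3, 7, 14 and 28 using Wilcoxon's test".

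**The concern.** The quantitative test on the trial's main specimen ignores a measurement that may well predict the outcome. Two things follow.

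First, if Day 0 load predicts later load, the unadjusted test is less precise than it could be at the same sample size, and a chance difference between arms at Day 0 passes into the Day 3 and Day 7 results. Randomization is stratified only by symptom duration (Protocol 5.1), so the design does not balance Day 0 load directly.

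Second, the change-over-time endpoint is tied to no particular analysis. Items a to d contain no change from Day 0 and no repeated-measures comparison. The only AUC that the SAP defines is for self-swabs, and the analysis linking shedding to symptoms is left to a later plan (SAP 4.9.1). The choice among a by-visit test, a change score and a model could therefore be made after the data are seen.

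**Working it through.** **1. The plan's own figure.** The documents give no power for the quantitative tests. The only stated calculation that bears on Day 3 is for the binary primary endpoint (Protocol 9.2.1): 42.5% v 57.5%, 90% power, two-sided Fisher's exact test, total 490, or 546 after 10% missing. This reproduces. Exact Fisher power at 245 per arm is 90.3%, and 245 / 0.9 = 272.2, rounded up to 273 per arm, gives 546. It neither supports nor contradicts the present point, but it supplies a design effect.

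**2. Inputs.**

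- Sample size: SAP 4.8 includes the 50 pilot subjects in secondary efficacy analyses, so 560 x 0.9 / 2 = 252 per arm, before any loss of unconfirmed cases.
- Share at the limit at Day 3: 50%, from the pooled detection rate in Protocol 9.2.1.
- Design effect on a latent normal scale: z(0.575) - z(0.425) = 0.189 + 0.189 = 0.378 SD.
- A smaller effect for contrast: 0.30 SD, which is about a 12-point difference in detection.
- Share below the limit at Day 7: not in the documents; 85% is assumed.
- Correlation rho between Day 0 and follow-up load: not in the documents; 0 to 0.6 is assumed.

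**3. Without censoring.** Baseline adjustment multiplies the variance by 1 - rho², and a change score multiplies it by 2(1 - rho). For a test with 80% unadjusted power (1.96 + 0.84 = 2.80), power becomes Phi(2.80 / sqrt(factor) - 1.96).

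| rho | Factor, adjusted | Power, adjusted | Factor, change score | Power, change score |
|---|---|---|---|---|
| 0 | 1.00 | 80% | 2.00 | 51% |
| 0.3 | 0.91 | 83.6% | 1.40 | 66% |
| 0.5 | 0.75 | 89.9% | 1.00 | 80% |
| 0.6 | 0.64 | 93.8% | 0.80 | 88% |

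A raw change score is worse than the follow-up value alone whenever rho is below 0.5.

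**4. With censoring.** Simulated at 252 per arm: bivariate normal Day 0 and follow-up values, follow-up values below the limit tied at the bottom, and an unadjusted Wilcoxon test against a Wilcoxon test stratified by Day 0 quartile (van Elteren).

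| Setting | Unadjusted power | Gain, rho 0.3 | Gain, rho 0.5 | Gain, rho 0.6 |
|---|---|---|---|---|
| Day 3, 50% at limit, 0.378 SD | 96-97% | about 1 | about 2 | about 2 |
| Day 3, 50% at limit, 0.30 SD | about 85% | about 2 | about 7 | about 9 |
| Day 7-like, 85% below limit, 0.378 SD | about 80% | about 2 | about 6 | about 7 |

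Gains are in percentage points. A second set of runs gave 0.5, 2.3 and 2.6 points for the first row and about 1, 4 and 7 for the third, so a point or two is simulation noise. At rho 0 the loss is under 1 point. Under no effect, with rho 0.5 and 50% at the limit, the rejection rate was 5.6% unadjusted and 5.2% stratified.

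**5. Chance imbalance.** The standard error of the Day 0 difference is sqrt(2 / 252) = 0.089 SD. A two-standard-error imbalance (0.178 SD) at rho 0.5 moves the expected latent follow-up difference by 0.5 x 0.178 = 0.089 SD, about a quarter of the 0.378 SD design effect (0.089 / 0.378 = 0.24).

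**The case against.** A reader might infer that the plan makes no use of Day 0 viral load at all, and that the change-over-time endpoint has no between-arm analysis. The documents do not support that. The PEP is defined by central PCR at Day 0 (SAP 4.1), and item d repeats every analysis in subjects detectable at Day 0. Items b and c do compare arms on post-baseline shedding, and item c compares an ordered Day 3/Day 7 pattern. These are valid comparisons under randomization. What remains true is that using Day 0 detectability to select subjects does not adjust for how much virus they carried.

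The documents also never say that the endpoint means change from Day 0. Protocol 7.3.4 uses similar words for the by-visit Tier 1 measurements, so the by-visit tests may be the intended analysis. That reading is fair, but the SAP does not state it.

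The 4.10 item g parallel is imperfect: that outcome is an AUC that includes the Day 0 value, whereas Day 3 and Day 7 values do not. It shows that the method is already in the SAP, not that the SAP is inconsistent.

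A stratified by-visit test is baseline adjustment. It is not a longitudinal analysis of change and should not be described as one.

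Finally, the gain is small where power is already high. At the design effect the unadjusted Day 3 test has about 96-97% power, and Protocol 9.2.1 regards differences below 15 points as unlikely to be clinically meaningful. This stands. The larger gains appear only at a smaller effect or with heavier censoring. An imbalance would also be visible in the Day 0 table, though seeing it does not correct for it.

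**Conclusion.** The point holds in a limited form. SAP 4.8.2 item b leaves out a baseline measurement that is already collected, and the SAP names no change-from-Day-0 or longitudinal comparison for a listed endpoint. The consequences are lost precision and exposure to chance Day 0 imbalance in a secondary analysis, not bias on average, inflated type I error or any effect on the primary result.

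The gain is conditional on an unknown correlation. For rho between 0.3 and 0.6 it is about 1 to 2 points at Day 3 under the design effect, about 2 to 9 points at 0.30 SD, and up to about 7 points in a Day 7-like case that also rests on an assumed censoring rate. If Day 0 load does not predict later load, the gain is nil and the cost is under 1 point. All of this assumes a latent normal model and 252 per arm. The case for acting rests on a near-zero cost and on fixing the analysis in advance, more than on a large gain in power.

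**What to change.** In SAP 4.8.2 item b:

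- Stratify the censored Wilcoxon comparisons at Day 3 and at Day 7 by quartile of Day 0 NP viral load.
- In the ITT, put subjects undetectable at Day 0 in the lowest stratum and those with no Day 0 result in a separate stratum.
- State that this is the baseline-adjusted analysis serving the change-over-time endpoint.
- Do not use a raw change score. It is poorly defined below LLOQ and loses power when the correlation is under 0.5.

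The cost is a sentence or two in the SAP and one strata term in the program, with no new data. If a true longitudinal analysis is wanted, it would have to be specified separately.
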